## 11.3 Methods of statistical analysis

Statistical analyses will be performed using all patients with evaluable data (e.g., pathologic staging among those who had a prostatectomy, and safety data among those who receive a dose of olaparib).

For efficacy analysis pathologic complete response is defined as the absence of morphologically identifiable carcinoma in the prostatectomy specimen, as evaluated by the site pathologist using standard methods. Formalin-fixed, paraffin-embedded slides will be evaluated by a central pathology review at completion of the study. Comparison of the actual pathologic complete response rate with the historial rate of 10%.

For safety analyses, all patients who received at least one dose of study drug and had at least one post-baseline safety assessment will be evaluated. Data will be descriptive, describing frequency of grade 1-5 adverse events. Data from all cycles of treatment will be combined in the presentation of safety data. AE will be listed individually by subject. The number of subjects experiencing each AE will be summarized by the Medical Dictionary for Regulatory Activities (MedDRA) system organ class, MedDRA preferred term and CTCAE grade. The number and percentage of subjects with adverse events in different categories (e.g. causally related, CTCAE grade ≥3 etc.) will be summarized. Any AE occurring before the first dose of investigational product (i.e. before study Day 1) will be included in the data listings but will not be included in the summary tables of adverse events. Any AE occurring within the defined 90 day follow-up period after discontinuation of olaparib will be included in the AE summaries. Hematology, clinical chemistry, vital signs, ECG data, demographic data, medical histories and concomitant medications will be listed individually by subject. For all laboratory variables, which are included in the current version of CTCAE, the CTCAE grade will be calculated. Summary statistics of mean, median, standard deviation, minimum, maximum and number of observations will be used. Details of any deaths will be listed for all subjects.

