# 1.4 Rationale for conducting this study

The frequency of HRD in prostate cancer increases substantially from the population of patients with localized prostate cancer to those with metastatic disease, reflecting the lethal phenotype mediated by HRD. Lethality is a reflection of early micrometastatic dissemination and an inability of local therapy alone to cure the disease. Men with localized prostate cancer with HRD either as a result of germline or somatic inactivation require better systemic therapy to improve their outcomes. The primary objective of this study is to assess whether the use of the PARP inhibitor olaparib prior to prostatectomy will result in pCR, which is credentialed in other malignancies as a surrogate for effective systemic elimination of tumor and long term cure. This is a pilot study to assess the feasibility of this approach in men with localized disease, with assessment of pCR, surgical margin status, extracapsular extension, seminal vesicle and nodal involvement, all of which are pathologic indicators of activity of neoadjuvant therapy. It is anticipated that the majority of patients will be known to be carriers of pathogenic germline variants, although a subset with purely somatic inactivation and HRD may identified in other ways. There is no evidence that tumors with germline vs. somatic inactivation will be differentially sensitive to PARP inhibition, so both populations will be eligible. A neoadjuvant PARP inhibitor study has not been performed in patients with prostate cancer and this study will also assess the safety and toxicity of olaparib in this patient population. If neoadjuvant therapy does not result in pCR, the remaining tissue is by definition resistant to therapy and remaining tumor tissue will be interrogated for mechanisms of resistance to inform future combination studies in advanced and localized HRD prostate cancer.

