## 1.5 Benefit/risk and ethical assessment

The risk/benefit associated with the use of olaparib administered prior to prostatectomy must weigh the risks of the drug, both acute and long term, vs. potential benefits. The justification for adding systemic therapy for patients with HRD prostate cancer is related to the significantly increased risk of relapse and death associated with HRD. Patients who are BRCA2 carriers have a 4-5 fold increased risk of developing prostate cancer . Once germline carriers are diagnosed with prostate cancer, their crude risk of metastasis and cancer specific mortality is increased approximately 8 fold . Although in multivariate analysis the overall risk of cancer specific mortality decreases, the presence of a germline mutation significantly increases the risk of being diagnosed with high risk or metastatic disease reflecting an aggressive biology . The frequency of other germline DNA repair genes is so low in the general population of men diagnosed with localized disease that no studies of their impact on relapse and cancer specific mortality has been carried out. Given the rarity of these variants in localized disease and the increased incidence in patients with metastatic disease. we anticipate that a similar increase in mortality attends the presence of these mutants . As noted, cancer specific relapse and death after definitive therapy is essentially always related to regional nodal or systemic metastasis, which can only be addressed with better systemic treatment. The relative risk/benefit calculation for treatment men with localized HRD prostate cancer with olaparib must balance risks of morbidity and mortality of the disease with toxicities of the therapy. The risks of cancer related morbidity and mortality are outlined above. The risks of olaparib outlined in section 1.2.2 and 1.2.3 are primarily myelosuppression, which in patients with advanced prostate cancer not receiving concurrent therapy was grades 1 or 2 and nausea and vomiting grades 1 or  $2^{20}$ . In other settings the frequency of more significant toxicities, including pneumonitis, myelodysplasia and leukemia are rare (Section 1.2) and MDS/leukemia frequency is confounded by prior therapy for the majority of patients (ovarian cancer) with the DNA damaging agent platinum, and known to cause MDS/AML at a very similar frequency in this patient population . There is no evidence from neoadjuvant studies of PARPi in patients with breast cancer that PARPi increases the risk of perioperative complications . The use of prostatectomy in this study as definitive therapy is appropriate as there is clear evidence that radiation and prostatectomy are at least equivalent with some studies suggesting better outcomes in high risk patients . The potential benefits of neoadjuvant PARPi for patients with HRD tumors could be reduced risk of relapse, metastasis or death which is significant in this patient population. This study will not formally evaluate long term outcomes but will provide pilot data regarding frequency of pCR, and improvement of other pathologic criteria which are predictive of relapse, as well as providing tissues which will allow interrogation of mechanisms of resistance if olaparib does not improve pCR rate.

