## 5.4.12.3 Interruptions for intercurrent non-toxicity related events

Study treatment dose interruption for conditions other than toxicity resolution should be kept as short as possible. If a patient cannot restart study treatment within 4 weeks for resolution of intercurrent conditions not related to disease progression or toxicity, the case should be discussed with AZ study physician.

All dose reductions and interruptions (including any missed doses), and the reasons for the reductions/interruptions are to be recorded in the eCRF.

Study treatment should be stopped 1 day before prostatectomy. No stoppage of study treatment is required for any needle biopsy procedure.

Study treatment should be discontinued for a minimum of 3 days before a patient undergoes radiation treatment. Study treatment should be restarted within 4 weeks as long as any bone marrow toxicity has recovered.

Because the AEs related to olaparib may include asthenia, fatigue and dizziness, patients should be advised to use caution while driving or using machinery if these symptoms occur.

Table 4 Dose reductions for study treatment

Initial Dose	Following re-challenge post interruption: Dose reduction 1	Dose reduction 2
300mg twice daily	250mg twice daily	200mg twice daily

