## Time period for collection of adverse events

Adverse events and SAE will be collected from the time of patient consent until 30 days after prostatectomy.

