## Follow-up of unresolved adverse events

Adverse events will be followed until resolution or until the investigator determines that the adverse event is not expected to return to baseline.

The following variables will be collected for each AE:

AE (verbatim)

The date when the AE started and stopped

NCI CTCAE grade and the maximum CTC grade attained

Whether the AE is serious or not

Investigator causality rating against the Investigational Product (yes or no)

Action taken with regard to investigational product/comparator/combination agent Outcome.

In addition, the following variables will be collected for SAEs:

Date AE met criteria for serious AE
Date Investigator became aware of serious AE
AE is serious due to
Date of hospitalization
Date of discharge
Probable cause of death
Date of death
Autopsy performed

Description of AE

Causality assessment in relation to Study procedure(s)

Causality assessment in relation to Other medication

It is important to distinguish between serious and severe AEs. Severity is a measure of intensity whereas seriousness is defined by the criteria in Section 6.3.3. An AE of severe intensity need not necessarily be considered serious. For example, nausea that persists for several hours may be considered severe nausea, but not a SAE. On the other hand, a stroke that results in only a limited degree of disability may be considered a mild stroke but would be a SAE.

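### No planned adverse event summary in 11.3 is split at prostatectomy, so postoperative events are counted together with events on olaparib

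*Combined protocol and SAP*

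**What the plan says.** Section 11.3 counts subjects with each AE by MedDRA system organ class, preferred term and CTCAE grade. It sets these rules on time:

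- Treatment cycles are pooled: "Data from all cycles of treatment will be combined in the presentation of safety data".
- Events before first dose "will be included in the data listings but will not be included in the summary tables of adverse events".
- For the period after treatment: "Any AE occurring within the defined 90 day follow-up period after discontinuation of olaparib will be included in the AE summaries".

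No table is divided at surgery. The section also plans a by-subject listing of every AE and summaries by category, with causally related and grade 3 or higher as examples. Laboratory data are to be listed and described with summary statistics. The text does not say that values taken before and after surgery are kept apart.

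On timing, section 5.4.12.3 says "Study treatment should be stopped 1 day before prostatectomy". Table 6 puts surgery on Day 90 with a window of 14 days either side. Section 6.3.4 says "Adverse events and SAE will be collected from the time of patient consent until 30 days after prostatectomy". Section 6.3.5 and Table 6 (footnote b) instead run follow-up for about 30 days after the last dose.

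Start and stop dates and a yes/no rating of causality to olaparib are collected for every AE. Causality to a study procedure is collected only for SAEs (follow-up of unresolved adverse events, within 6.3.4).

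**The concern.** Section 1.4 says no neoadjuvant PARP inhibitor study has been done in prostate cancer and that "this study will also assess the safety and toxicity of olaparib in this patient population". The safety tables are where that assessment will be read.

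Every man who follows the plan has a major operation the day after his last dose. Table 1 lists anaemia, nausea, vomiting and fatigue as very common olaparib reactions. That the same events can follow radical prostatectomy is ordinary clinical knowledge, taken here as an assumption. Because the tables count subjects per term, a man whose only anaemia was postoperative adds to the same cell as a man who became anaemic on drug.

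A reader who takes the all-causality table as tolerability over 90 days of olaparib would see rates that are too high for such terms. Nor does any planned summary show the postoperative period alone. Section 1.5 considers that period, but from another disease: "There is no evidence from neoadjuvant studies of PARPi in patients with breast cancer that PARPi increases the risk of perioperative complications".

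**Working it through.** The plan states no safety figure to reproduce. Its one design calculation (section 11.2, 15 patients for the pCR rate) is not involved.

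**Step 1. Does the follow-up fall after surgery?** The last dose is one day before prostatectomy (5.4.12.3; Table 6 footnotes). For a man who completes treatment, all but about the first day of any post-discontinuation window is therefore the day of surgery or later. This does not hold for a man who stops olaparib early and is operated on later.

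**Step 2. Which sentence brings those events in?** The cycles sentence concerns treatment cycles, and surgery is not a cycle. The operative rule is the 90-day sentence in the same section. Together with the absence of any boundary other than first dose, it puts on-treatment and postoperative events in the same cells.

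**Step 3. How much of the summarised time is postoperative?** Share = F / (S + F), where S is the day of surgery and F the days of follow-up, ignoring the one-day offset.

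| Day of surgery S | F = 30 (section 6.3.4) | F = 90 (section 11.3) |
|---|---|---|
| 76 | 30/106 = 28% | 90/166 = 54% |
| 90 | 30/120 = 25% | 90/180 = 50% |
| 104 | 30/134 = 22% | 90/194 = 46% |

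The two columns differ because the documents do. Section 6.3.4.1 removes any duty to report new AEs actively after the scheduled follow-up, apart from named exceptions. Days 31 to 90 would therefore be incompletely observed, and the share as collected is likely to be nearer 25% than 50%.

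**Step 4. Direction of the effect.** Let a be the proportion of men with a given term on treatment and b the proportion with it after surgery. The pooled table shows the proportion with it in either period, which cannot be below a. It exceeds a whenever at least one man has the term only after surgery.

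**Step 5. Size.** The documents give no value of b and no AE rates for this setting, so the size cannot be derived from them. For illustration only, assume independence between periods and that all men have surgery: pooled = 1 − (1 − a)(1 − b).

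- a = 20%, b = 10%: 1 − 0.80 × 0.90 = 28%. In 15 men, 4.2 expected instead of 3.0.
- a = 10%, b = 40%: 1 − 0.90 × 0.60 = 46%. In 15 men, 6.9 instead of 1.5.
- Over a from 10% to 40% and b from 10% to 80%, the pooled figure runs from 19% to 88%.

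The range is that wide because b is unknown. It shows how far the pooled figure depends on an unstated quantity; it does not estimate the bias.

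**The case against.** The strongest reply is that nothing is lost. Every AE is dated and listed by subject, a causally related summary is planned, and the category list in 11.3 is open-ended. AE reviews at the Day 90 visit and at the end of study lie either side of surgery. With a target of 15 men, anyone can sort the listing by date. The study is a descriptive pilot, safety is not among the objectives in 2.1 to 2.3, and the remark on perioperative risk in 1.5 is background, not a commitment to measure complications. Table 1 reports adverse drug reactions, whose nearest counterpart here is the causally related summary.

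Much of this stands. A reader might infer that neither olaparib's tolerability nor perioperative safety could be read from this trial. The documents do not support that: the listings, dates and causally related summary allow a partial separation, and procedure causality is recorded for SAEs. A reader might also take the sentence on cycles as an instruction to merge periods around surgery; it is not one. Nor can a fourfold inflation be claimed, since the 10% and 40% in the illustration are assumptions.

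What does not stand is that the existing features make a split unnecessary. The causally related summary rests on one yes/no judgement in an uncontrolled, open-label study. That judgement is hardest for an event arising days after both the last dose and the operation. Sorting the listing afterwards is possible but not planned. Section 1.4 does commit the study to assessing safety and toxicity, even though section 2 does not list it.

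**Conclusion.** The point holds in this form: no planned summary separates on-treatment from postoperative AEs. Following 11.3 as written mixes them in the all-causality counts for overlapping terms. For men who complete treatment, the postoperative part is about 25% of the summarised time on the 30-day collection period, or about 50% on the 90-day window, with surgery on Day 90. For terms that occur in both periods the counts would overstate on-treatment toxicity. The direction follows from counting subjects over a longer window; the amount cannot be quantified from the documents.

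This rests on two assumptions: that the overlapping terms do occur after prostatectomy, and that most men complete treatment and have surgery. The pCR analysis, sample size, alpha and power are unaffected. It is a cheap improvement to the safety reporting, and worth making before the data are summarised.

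**What to change.** In section 11.3:

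1. Keep the overall AE table and add the same tables for two periods, assigned by date of onset or worsening: first dose to the day before prostatectomy, and day of prostatectomy to the end of AE collection. Men without surgery contribute to the first period only, so the second has its own denominator.
2. Summarise end-of-study (postoperative) laboratory values separately from on-treatment values.
3. Reconcile the 90-day summary window with the 30-day collection periods in 6.3.4 (from prostatectomy), 6.3.5 and Table 6 (from last dose), so that the tables cover a period in which AEs are actually collected.

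The start date is already collected. The date of worsening is not named among the AE variables in 6.3.4, so the plan should say how a rise in grade after surgery is dated, for example as a new record. The cost is one further set of tables, with small counts in each period. Recording causality to the procedure for non-serious AEs would help interpretation but is optional and not needed for this fix.

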Starting on Day 1, all patients will ingest olaparib (300 mg twice daily) at the same times each day, without breaks (except as outlined for toxicity), for 90 days. The 90 day duration is chosen as a duration adequate to assess impact of neoadjuvant therapy on downstaging but not so prolonged that if patients do not respond to therapy, that potentially curative local therapy is being significantly delayed. Multiple studies have demonstrated in unselected populations that 90 day delay to surgery is not associated with any change in long term outcomes . During neoadjuvant therapy, dose reduction of olaparib is allowed for toxicity as detailed in the protocol. Patients should receive olaparib until 1 day prior to prostatectomy, until the

patient can no longer tolerate the treatment due to an adverse event, until the patient initiates another systemic antineoplastic drug or an investigational drug, or at the discretion of the Investigator. Safety and tolerability will be documented throughout the study and 30 days after prostatectomy by assessment of adverse events, vital signs, and laboratory assessments as defined in the Schedule of Activities. All adverse events will be monitored and recorded until the Safety Follow-up visit. Adverse events will be graded according to the National Cancer Institute Common Terminology Criteria for Adverse Events, Version 4.03 (NCI-CTCAE v4.03). In the event a patient discontinues olaparib due to a related adverse event, follow up will continue until adequate resolution of the adverse event, the physician deems the adverse event to be stable, the patient initiates another systemic antineoplastic drug or an investigational drug, or the patient withdraws consent from the study. A safety follow-up visit will be conducted approximately 30 days after the last dose of olaparib or before the initiation of a new systemic antineoplastic therapy or investigational agent, whichever occurs first. Any ongoing adverse event thought to be related to study treatment will be followed until the event has resolved to baseline grade, the event is assessed by the Investigator as stable, the patient initiates another systemic antineoplastic drug or an investigational drug, the patient is lost to follow-up, the patient withdraws consent, or it has been determined that study treatment or participation is not the cause of the adverse event.

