#### 6.3.4.1 Adverse events after the 30 day follow up period

For Pharmacovigilance purposes and characterization, any case of MDS/AML or new primary malignancy occurring after the 30 day follow up period should be reported to AstraZeneca Patient Safety whether it is considered a non-serious AE (e.g., non-melanoma skin cancer) or SAE, and regardless of investigator's assessment of causality or knowledge of the treatment arm. Investigators will be asked during the regular follow up for overall survival if the patient has developed MDS/AML or a new primary malignancy and prompted to report any such cases.

At any time after a patient has completed the study, if an Investigator learns of any SAE including sudden death of unknown cause, and he/she considers there is a reasonable possibility that the event is causally related to the investigational product, the investigator should notify AstraZeneca, Patient Safety.

If patients who are gaining clinical benefit are allowed to continue study treatment post data cut off and/or post study completion then all SAEs must continue to be collected and reported to Patient Safety within the usual timeframe.

Otherwise, after study treatment completion (i.e. after any scheduled post treatment follow-up period has ended) there is no obligation to actively report information on new AEs or SAEs occurring in former study patients. This includes new AEs/SAEs in patients still being followed up for survival but who have completed the post treatment follow up period (30 days).

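### Section 11.3 summarises adverse events over a 90-day post-olaparib period that is defined nowhere; general collection of new events is planned for 30 days, counted from surgery in some places and from last dose in others

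*Combined protocol and SAP*

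**What the plan says.** The analysis rule is in section 11.3: "Any AE occurring within the defined 90 day follow-up period after discontinuation of olaparib will be included in the AE summaries". The same section lists AEs by subject and makes the safety presentation descriptive.

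The sections that govern collection give 30 days, from two different anchors.

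- **Counted from prostatectomy.** Section 6.3.4, under the heading on the collection period: "Adverse events and SAE will be collected from the time of patient consent until 30 days after prostatectomy". Section 3.2 agrees in one sentence: "Safety and tolerability will be documented throughout the study and 30 days after prostatectomy".
- **Counted from last dose.** Section 3.2, in another sentence: "A safety follow-up visit will be conducted approximately 30 days after the last dose of olaparib", or before a new systemic antineoplastic or investigational agent if that comes first. Section 3.2 also has all AEs recorded until that visit. Table 6 footnote b times the visit in the same way, with a tolerance of 5 days. Section 6.3.5 requires follow-up of existing and new AEs for 30 calendar days after last dose and/or until resolution. The Deaths paragraph of section 6.3 uses 30 days after last dose.
- **No precise anchor.** Section 6.3.4.1 gives the post-treatment follow-up as 30 days and says that afterwards "there is no obligation to actively report information on new AEs or SAEs occurring in former study patients".

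The exceptions in section 6.3.4.1 are MDS/AML, new primary malignancy, serious events the investigator considers causally related to the drug, and serious events under continued treatment. Section 6.3.2 also requires any AE of special interest, which includes pneumonitis, to be reported and states no time limit. Section 5.4.5 fixes the end-of-study visit at Day 120 ± 5.

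**The concern.** Section 11.3 treats the 90-day period as already defined, but a reader who looks for the definition finds only 30-day windows. In other sections, 90 days or Day 90 is the treatment length, a tolerable surgical delay, a clinic visit or the date of surgery. The three-month period after last dose concerns contraception, sperm donation and conception.

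The mismatch matters because ascertainment changes partway through the window. For about 30 days new AEs of every kind are collected. After that only selected kinds of new event are reported. Counts pooled over both stretches and labelled as 90 days could be read as a 90-day incidence, and would understate it.

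The split anchor adds a second problem for men who stop olaparib early. Section 5.7.1 sends a man who has been off drug for a continuous month on to prostatectomy. Under the last-dose anchor his window may have closed by the day of surgery; under the prostatectomy anchor it runs for 30 days afterwards. If he has been dosed and is evaluable for toxicity, he belongs to the safety set (section 11.1.2), even if he is replaced for efficacy under section 5.8. Assessing safety and toxicity in this population is a stated aim (section 1.4), and with about 15 men planned (section 11.2) a few events visibly move a percentage.

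**Working it through.** **Inputs**

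- Surgery on Day S, with S = 90 ± 14, so 76 to 104 (section 5.4.4; Table 6 footnotes).
- Last dose on Day L, with L = S − 1 on the planned course (section 5.4.12.3; Table 6 footnotes).
- Summary window ends on L + 90 (section 11.3).
- General collection of new AEs ends on S + 30 (section 6.3.4) or L + 30 (section 6.3.5).
- End-of-study visit on nominal Day 120 (section 5.4.5).

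The plan gives no derivation of the 90 days, so there is no calculation of its own to reproduce.

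**Planned course**

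Summary end = (S − 1) + 90 = S + 89. Collection end = S + 30, or (S − 1) + 30 = S + 29. The gap is therefore 89 − 30 = 59 days or 89 − 29 = 60 days, whatever the permitted surgery day. As a share of the window, 59/90 = 65.6% and 60/90 = 66.7%.

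| Surgery day | Last dose | Last dose + 30 | Surgery + 30 | Last dose + 90 | Days from the Day 120 visit to the end of the 90-day window |
|---|---|---|---|---|---|
| 76 | 75 | 105 | 106 | 165 | 45 |
| 90 | 89 | 119 | 120 | 179 | 59 |
| 104 | 103 | 133 | 134 | 193 | 73 |

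The gap between the stated windows is constant, but the stretch after the last scheduled visit is not, because section 5.4.5 fixes that visit by study day. For surgery on Day 104, Day 120 is only 120 − 104 = 16 days after the operation.

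**Early stop, first illustration** (assumed: last dose Day 59, surgery Day 90)

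- Last-dose window ends: 59 + 30 = Day 89, the day before surgery.
- Prostatectomy window ends: 90 + 30 = Day 120, which is 31 days later.
- Summary window ends: 59 + 90 = Day 149, which is 149 − 120 = 29 days after collection under section 6.3.4 ends.

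**Early stop, second illustration** (assumed: last dose Day 20, surgery Day 90)

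- Summary window ends: 20 + 90 = Day 110.
- Collection under section 6.3.4 ends: 90 + 30 = Day 120.
- AEs on Days 111 to 120 are collected but lie outside the stated summary rule.

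In general, collection outlasts the summary window when S + 30 > L + 90, that is, when S − L > 60 days. Section 5.7.1 sets no upper limit on the time from last dose to surgery.

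**The case against.** The strongest reply is that section 11.3 is only an inclusion rule. It promises no 90-day incidence, the tables are descriptive, and the primary endpoint is untouched. AEs are listed by subject and their start and stop dates are recorded (follow-up paragraph under section 6.3.4), so any window can be rebuilt for events that were collected. This stands and limits the severity. It does not recover new events that nobody was asked to collect.

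A second reply is that the anchors differ by one day on the planned course, against a visit tolerance of 5 days, and that some of the last-dose text governs visits or death reporting rather than AE collection. That is fair. But section 6.3.5 concerns AEs directly, and section 3.2 records all AEs only until a visit timed from last dose, so a conflict with section 6.3.4 remains.

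Several stronger readings are tempting but are not supported.

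- *Nothing is captured after 30 days.* Selected new events are still reportable under sections 6.3.2 and 6.3.4.1, and existing AEs are followed to resolution.
- *Early stoppers' postoperative events are lost.* Section 6.3.4 would still collect them for 30 days, and the Day 120 visit would cover part or all of that time. The documents disagree; they do not exclude these events.
- *Late MDS/AML will be missed.* Section 6.3.4.1 says "Investigators will be asked during the regular follow up for overall survival if the patient has developed MDS/AML or a new primary malignancy", while neither section 5.4 nor Table 6 schedules survival follow-up and section 1.5 says "This study will not formally evaluate long term outcomes". The duty to report such cases nevertheless stands without the prompt.
- *The timetable rules out 90 days.* Section 9.4 gives a projection, not a data cut-off.
- *The prostatectomy anchor is the intended one.* The documents do not show which anchor is meant.

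The opposite inference, that a longer summary window can never leave out a collected AE, also fails once surgery is more than 60 days after last dose.

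**Conclusion.** The inconsistency is real, and its effect is minor. Section 11.3 relies on a 90-day period that no section defines, while every general post-treatment AE, serious AE or death window is 30 days. For a man who doses to the day before surgery, 59 to 60 of the 90 days (66% to 67%) fall outside general collection of new AEs, so a table labelled 90 days could understate incidence. For a man whose surgery is more than 60 days after last dose, the mismatch runs the other way.

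The anchor split is worth one day on schedule and about a month or more after an early stop followed by surgery. In that case the sections disagree on whether new postoperative AEs are collected.

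The planned-course figures rest only on the stated schedule. The two early-stop examples use assumed days, and the documents give no early-stop rate, so the number of men affected cannot be stated. The consequence is confined to descriptive safety tables in about 15 men, with listings and AE dates as partial mitigation.

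**What to change.** 1. In section 11.3, replace the 90-day window with the window over which AEs are generally collected, and check that it covers everything collected.
2. Show later events reported under section 6.3.4.1 separately, labelled as selectively ascertained.
3. Reconcile section 3.2, section 5.4.5, section 6.3.4 and its follow-on 6.3.4.1, the Deaths paragraph, section 6.3.5 and Table 6 footnote b to one stated length and one end anchor. Say how the cut-off at a new systemic antineoplastic or investigational agent applies. The sponsor must choose the anchor.
4. If a 90-day summary is really intended, extend the collection text and the visit schedule to match instead.

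Steps 1 to 3 cost wording and, depending on the anchor chosen, possibly a later last contact for men who stop early and then have surgery. Step 4 would add about 59 to 60 days of AE collection per man on the planned course.
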